Description of Study Populations: A total of 60 individuals (males and females) between the ages of 21-60 will be enrolled in the study. Two participant populations will be recruited into this protocol. Participant populations are individuals with the following conditions: 1.) current suicidal ideation and past suicide attempt under intranasal ketamine (Group 1, n= 30) and current suicidal ideation and past/recent suicide attempt under placebo (Group 2, n= 15). Group 1 will include two subgroups, with (n=15) or without (n=15) recent abuse of alcohol plus positive personal/family history for alcoholism. The study will take place at a Research Unit at the Harris County Psychiatric Center, UT Houston. Participants at acute risk will be admitted to the HCPC 2D Unit, a secure, but voluntary psychiatric unit, in which there will be nursing staff and physicians available at all hours to respond to any crisis as needed. Subjects will complete an informed consent process and will be systematically screened for inclusion and exclusion criteria. Only participants with a lifetime history of suicide attempt will be enrolled.

Design

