This study will be a double-blind, randomized, placebo controlled trial, evaluating drug-free inpatients (at least 24hs period pre-admission) with depressive episode associated with past suicidal attempt and current active suicidal ideation. Patients will be randomly assigned to intranasal ketamine hydrochloride (50 mg) or saline solution (1 to 1 in both groups, suicide or suicide plus alcohol, with a total of 4 groups). After the single intranasal administration, assessments will occur at +40 min, +240 min, +24 h (phase 1), and +48 h (phase 2). For phase 2, patient may receive their regularly scheduled daily medications if improvement less than 50%. Pts will be subsequently followed up on the suicidal ideation scores until discharge once a day with treatment as usual. This study is expected to take one year to be concluded. Medication should be applied in the first 24hs after admission. There is no approved treatment for suicidal ideation and just a few trials used ketamine for suicidal ideation, none of them evaluating the intranasal route. Thus, a placebo-controlled study is warranted to prevent potential methodological issues. The use of ketamine plus standard care would bias the evaluation of the specific antisuicidal efficacy of intranasal ketamine since standard treatments in some cases may also target suicidality and mood in the short-term.

Assessment of antisuicidal efficacy will be obtained using the Columbia-Suicide Severity Rating Scale (CSSRS) as a screening tool for inclusion (based on "yes" or "no" questions) at HCPC. MADRS item 10 score of 5 or 6 suggests active suicidal risk and will be also used as the threshold for patient inclusion in the ketamine intervention. For those enrolled, the primary efficacy outcome measure will be changes in suicide severity at 24hr post-treatment based on the Scale for Suicide Ideation (SSI) scores, which assesses presence of suicidal ideation and history of suicidal behavior. Secondary outcomes to be administered at each visit include the Montgomery-Åsberg Depression Rating Scale (MADRS), the Young Mania Rating Scale (YMRS), the Clinician-Administered Dissociative States Scale (CADSS), Snaith-Hamilton Pleasure Scale (SHAPS) Alcohol Urge Questionnaire (AUQ) and the Clinician-Administered National Institutes of Health-Brief Fatigue Inventory (NIH-BFI). Inter-rater reliability will be assessed for all ratings, with accepted kappa over 0.8.

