Potential psychotomimetic, dissociative, hemodynamic, and general adverse effects associated with ketamine will be also measured. Safety and tolerability will be specifically assessed the Clinician-Administered Dissociative States Scale (CADSS) and the mood item of the Young Mania Rating

IRB NUMBER: HSC-MS-17-0903
IRB APPROVAL DATE: 10/09/2019

Scale (YMRS). Clinically significant changes will be characterized as systolic or diastolic blood pressure (BP) >180/100 mmHg or heart rate >110 beats/minute.

Clinician Administered Measures

- 1) The *Scale for Suicide Ideation* (SSI) is a 21-item clinician-administered scale designed to quantify the intensity of current conscious suicidal ideation in various dimensions of self-destructive thoughts or wishes: the extent of the wish to die, the desire to make an actual suicide attempt, and details of any plans; also, internal deterrents to an active attempt, and subjective feelings of control and/or courage regarding a proposed attempt. Individuals are asked to report their current and worst-point suicidal thoughts (Beck et al 1979).
- 2) The *Columbia Suicide Severity Rating Scale* (C-SSRS) is a widely used measure of suicidal ideation and behavior. The “Screening/Baseline” version of the measure evaluates suicidal ideation and behavior both lifetime and in the last six months. The “Since Last Visit” version assesses suicidal thoughts and behavior since the last assessment. The C-SSRS takes 15 minutes to administer (Posner et al 2011).
- 3) Montgomery-Asberg Depression Rating Scale (MADRS) is a widely-used ten item instrument evaluating depressive symptoms in adults. The estimated time to completion is 20 minutes. Interrater reliability is high and scores correlate significantly with those of other validated depression measure, e.g. HDRS. Each of the ten items is rated on a scale of 0-to-6, with differing anchors describing escalating psychiatric severity (Montgomery et al 1979).
- 4) *Young Mania Rating Scale* (YMRS) consists of 11 items used to assess hypomanic/manic symptoms. The time for administration is 15-30 minutes (Young et al 1978).

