2. Able to provide written informed consent
3. Current suicidal ideation and depressive symptoms and DSM-IV-TR depressive episode (also MADRS score $\rightarrow 12$).
4. DSM-IV-TR criteria for current alcohol abuse (but not intoxicated/withdrawal, abstinent from drinking for > 5 days prior to admission).
5. Lifetime history of suicide attempt (patient)
6. Not taking any medication in the last 24hs.
7. SSI score over 4 (first five items) and Columbia scale score 4 or 5

Exclusion Criteria:

- Unstable medical condition or medical problem with known CNS effects, e.g. uncontrolled hypertension ($SBP \geq 170$ and/or $DBP \geq 100$) or recent history (6 months) of alcohol-withdrawal seizures or significant abnormal laboratory tests (LFT 3 times higher than normal).
- Currently having a manic episode.
- Prior diagnosis of a DSM-IV-TR psychotic spectrum disorder a personality disorder or current psychotic symptoms.
- Currently under the acute effects of an illicit substance.
- Pregnant or nursing women.

As the only public-academic teaching psychiatric hospital in Houston, Texas, the University of Texas Harris County Psychiatric Center serves a large and diverse patient population. Last year, HCPC served 2443 adult psychiatric patients who had a primary diagnosis of BD (35.2% of patients served) and a similar number with MDD. More than half (52.2%) of the patients admitted to HCPC were on suicide precautions, and the mean patient length of stay was 8.8 days. We estimate being able to assess approximately 1200 patients per year ($n = 3600$) for study eligibility and recruitment.

Regarding the recruitment strategy, we will only recruit participants who seek care for suicidal thoughts or behaviors at the HCPC. Recruitment strategies will not include local advertising in any type of media. Potential participant will be seen by a treating clinician who will complete routine assessment according to standards of care for their facility. Study staff will speak with clinician in person on site in the

IRB NUMBER: HSC-MS-17-0903
IRB APPROVAL DATE: 10/09/2019

emergency department or at the research unit. Study staff will review the Inclusion/Exclusion Checklist and Study Summary. If potential participant appears eligible for study, study staff will speak with potential participant in person. Study staff will again re-review Inclusion/Exclusion Checklist with the potential participant to assess eligibility and interest in the study.

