Our outcome analyses will focus on examining the acute effects and duration of intranasal ketamine treatment during inpatient psychiatric hospitalization. As a primary outcome, we will examine the efficacy of intranasal ketamine for preventing suicidal behavior and ideation among adult patients in a current depressive episode at day 1. Our primary outcome analysis seeks to answer two questions: 1) will intranasal ketamine work acutely compared to placebo, and 2) how long will this effect persist? Effect sizes will be calculated for intranasal ketamine treatment. In the primary outcome analysis, two dichotomous primary outcome measures will be examined in the evaluation: 1) the presence or absence of suicidal ideation, and 2) the presence or absence of suicidal behavior as measured using the C-SSRS and SSI. Our secondary outcome analysis will include an examination of 1) the effects of intranasal ketamine for suicidal ideation while controlling for improvements in depression and other dimensions 2) the potential role of recent alcohol abuse and previous alcohol dependence in the rapid anti-suicidal effects of intranasal ketamine. The symptom severity ratings of SSI, the C-SSRS total score and, as well as changes in MADRS scores will be utilized as primary and secondary outcomes, respectively. Normality assumptions for continuous variables will be examined. Baseline characteristics will be compared between responders and non-responders with the Mann-Whitney U test for continuous variables and the chi-square test for categorical variables. Changes between two time-points for continuous variables were tested with paired t tests, and associations between continuous variables will be quantified with the Spearman correlation coefficient. Random effects models will be performed to quantify changes in clinical score and its component items over time and to compare temporal differences between eventual responders and non-responders.

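### Presence or absence of suicidal behavior at day 1 cannot separate ketamine from placebo as a primary outcome, and the two C-SSRS forms do not support within-arm change from baseline

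*Combined protocol and SAP*

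**What the plan says.** The Statistics section sets day 1 as the time of the primary outcome, asks whether ketamine works against placebo and for how long, and names two dichotomous primary measures. The first is suicidal ideation. The second is "the presence or absence of suicidal behavior as measured using the C-SSRS and SSI". It also names the C-SSRS total score as an outcome, and it plans paired t tests for change between two time points in continuous variables.

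Clinician Administered Measures, item 2, describes two forms of the C-SSRS. Of the form meant for entry to the trial it says: "version of the measure evaluates suicidal ideation and behavior both lifetime and in the last six months". The follow-up form has a much shorter reach, in these words: "version assesses suicidal thoughts and behavior since the last assessment". No section says which form or look-back supplies which outcome.

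On eligibility, Description of Study Populations states: "Only participants with a lifetime history of suicide attempt will be enrolled". The inclusion criteria repeat this and add "SSI score over 4 (first five items) and Columbia scale score 4 or 5". Patients at acute risk are admitted to a secure unit, and Potential Benefits says that all suicidal patients are on active suicide watch.

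The Design section gives a different primary, the change in SSI at 24 hours. It describes the C-SSRS as a screening tool and omits it from the measures given at each visit. Study Procedures schedules ratings of suicidal thoughts at baseline, 40 and 240 minutes, day 1 and day 2 without naming the instrument. Data and Safety Monitoring uses the C-SSRS for frequent risk monitoring.

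**The concern.** A dichotomous primary outcome is useful only if it can differ between the arms. Behavior at day 1 has two natural readings here, and neither can differ by much. Under a lifetime look-back, eligibility fixes it at present for everyone. Under a since-last-visit look-back, the inpatient setting makes it absent for almost everyone. The SSI does not settle the matter, because the Design section describes it as covering the history of suicidal behavior, which every entrant has. The result on this primary would be decided by an unstated choice of form rather than by treatment, and a finding of no behavior in either arm could be misread as prevention.

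The second concern is narrower. If someone compares the baseline C-SSRS with a later one within an arm, the look-back shrinks from months or a lifetime to hours. The score can then fall for that reason alone.

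**Working it through.** **The plan's own sample size.** Inputs from Statistics: response 60% versus 10%, two-sided alpha 0.05, power 0.80. The unpooled two-proportion formula gives (1.960 + 0.842)² × (0.6×0.4 + 0.1×0.9) / 0.5² = 10.36, rounded up to 11 per group. The plan's figure reproduces. It rests on response rates from depression trials, so it says nothing about power for suicidal behavior.

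**Lifetime look-back.** A lifetime attempt is required, so prevalence is 100% in both arms and the between-arm difference is 0 by eligibility.

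**Since-last-visit look-back: number of events.** The documents give no 24-hour rate, so I assume p = 0.2% to 1%. Total n is 45 (the listed groups, 30 + 15) or 60 (the stated total).

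| n | p | Expected events, n × p | P(no event), (1 − p)ⁿ |
|---|---|---|---|
| 45 | 0.2% | 0.09 | 0.91 |
| 45 | 1% | 0.45 | 0.64 |
| 60 | 0.2% | 0.12 | 0.89 |
| 60 | 1% | 0.60 | 0.55 |

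**Since-last-visit look-back: power.** The plan names no test for this contrast. I used Fisher's exact test, two-sided at 0.05, because the expected counts are so small. The documents conflict on total and allocation, so I show three layouts: 30:15 as listed, 30:30 for 60 patients at 1:1, and 40:20 for 60 patients at about 2:1. With no ketamine events, significance first appears at this many placebo events:

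- 30:15 needs 3 (p = 0.032; 2 events give 0.106).
- 30:30 needs 6 (p = 0.024; 5 events give 0.052).
- 40:20 needs 3 (p = 0.033; 2 events give 0.107).

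Power is then the binomial probability of at least that many placebo events:

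| Ketamine vs placebo (assumed) | 30:15 | 30:30 | 40:20 |
|---|---|---|---|
| 0% vs 2% | 0.3% | <0.1% | 0.7% |
| 0% vs 5% | 3.6% | 0.3% | 7.5% |
| 0% vs 10% | 18% | 7% | 32% |

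The last two rows assume placebo rates 5 to 50 times the 0.2% to 1% range, and power is still far below 80%.

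**Within-arm change.** Six months is about 182.5 × 24 = 4,380 hours. If the C-SSRS were rated at +240 minutes and again at +24 hours, the later window would be 24 − 4 = 20 hours, a ratio of 219. On the lifetime column, behavior starts at 100%. With an assumed post-dose rate of 0% to 5%, it falls by 95 to 100 percentage points in each arm with no drug effect. As an illustration only, since the plan does not schedule this test, an exact McNemar test with every patient going from present to absent gives 2 × 0.5¹⁵ = 0.00006 at n = 15.

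**Between-arm effect of the window change.** With the same post-dose rate in both arms, the difference in change is (p − 1) − (p − 1) = 0. The shift is shared and cancels.

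**The case against.** A reader might infer that the C-SSRS outcomes, including the behavior primary, improve in both arms by construction, and that this hides the ketamine effect. The documents do not support that. The primary question is ketamine against placebo, presence or absence is not defined as change from baseline, and an offset shared by randomized arms cancels. No C-SSRS change score is specified: the Statistics section attaches change to the MADRS, and the paired t test sentence is general to continuous variables. Nor are the two forms assigned to visits; their use before and after dosing is inferred from their names.

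Ideation also need not fall to a floor. Entrants have current ideation, can still score 4 or 5 after dosing, and a since-last-visit window counts ideation that has already resolved, which pushes toward present. The SSI-change primary in the Design section does not depend on any C-SSRS window.

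It is fair to add that rarity and window mismatch are separate defects. Behavior would be too rare at 24 hours even with matched windows, and the event rates above are assumptions. The 100% figure belongs to the lifetime column and is not guaranteed for the six-month column.

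All of this stands and limits the second concern to within-arm comparisons. It does not rescue the behavior primary.

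**Conclusion.** The point holds on two counts of unequal weight.

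First, suicidal behavior at day 1 cannot work as a primary outcome. The lifetime reading is fixed at 100% by eligibility, which needs no assumption. The since-last-visit reading depends on an assumed event rate. At 0.2% to 1% there is a 55% to 91% chance of no event in the whole trial, and at 0% versus 5% power is below 8% in every layout that the documents allow.

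Second, a within-arm comparison of the baseline C-SSRS form with a later one would tend to show improvement regardless of treatment. The generic paired tests allow such a comparison but do not specify it. For lifetime behavior the fall is close to complete; for ideation it is a tendency whose size the documents do not let one calculate. The randomized contrast and the SSI-change primary are unaffected.

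This should be changed before analysis, but it does not undermine the trial's main SSI comparison.

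**What to change.** - Remove suicidal behavior from the primary outcomes in Statistics, and list any events by arm as safety.
- Take presence or absence of ideation at 24 hours from one named instrument: the SSI, using the current rating and not the worst-point rating.
- Use the lifetime/six-month C-SSRS form for eligibility only.
- If the C-SSRS stays as an outcome, add it by name to the +24 h and +48 h ratings in Design and Study Procedures. State the form and look-back at each, and compare arms over the same post-dose window.
- Exclude the C-SSRS from the paired tests of change from the baseline form.

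The cost is mainly protocol wording, plus two named C-SSRS ratings if it is kept (the protocol gives 15 minutes per administration). There are two downsides. The trial no longer claims prevention of suicidal behavior, which it could not have shown. And a +24 h C-SSRS window that reaches back to dosing may count ideation from before the drug acts, which could mask a rapid effect; for that reason current SSI should carry the ideation outcome.

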**A Randomized, Double-Blind, Placebo-Controlled Trial of the Rapid Antisuicidal Effects of
Intranasal Ketamine in Comorbid Depression and Alcohol Abuse**

NCT03539887

Version Date: 10/09/2019

IRB NUMBER: HSC-MS-17-0903
IRB APPROVAL DATE: 10/09/2019

A Randomized, Double-Blind, Placebo-Controlled Trial of the Rapid Antisuicidal Effects of Intranasal Ketamine in Comorbid Depression and Alcohol Abuse

Principal Investigator: [name], PhD, MSc.

Co-Principal Investigators: [name], [name], PhD.

Co-Investigators: [name] [name], [name] [name], MSc., [name], [name] MD, [name] MD, [name] MD, [name] MD.

General Information

Clinicians have a limited ability to predict imminent suicidal behavior and efficacious treatments are not available to treat suicidal patients. Thus, Rapid-acting treatments for suicidal individuals are truly needed. This project aims to evaluate the potential rapid and sustained antisuicidal and antidepressant effects of a single intranasal dose of ketamine in inpatients during a mood episode (in Major Depressive Disorder, MDD or Bipolar Disorder, BD) with or without comorbid recent abuse of alcohol. These results will elucidate the antisuicidal effects of ketamine using the intranasal route along with the identification of associated mediators or moderators; this approach has the potential for enormous public health impact.

Background

Suicide: A Major Public Health Problem

Suicide occurs across demographics and psychiatric disorders, killing at least one million individuals worldwide each year. In contrast to other injury-related death such as homicide or motor vehicle accidents, suicide rates have increased, particularly among middle-aged adults. In the US, each year, hundreds of thousands of Americans seek emergency treatment for suicidal thoughts or behaviors. Unfortunately, even when these individuals are hospitalized on inpatient units or connected with longterm psychiatric resources, they remain at acute risk for suicidal behavior. Over 40,000 Americans killed themselves in 2013 and over 380,000 presented to emergency services for suicidal thoughts and behaviors. In contrast, other forms of preventable death, such as motor vehicle accidents, have declined making suicide the leading cause of injury-related death in the U.S, and arguably, the leading cause of psychiatry-related mortality (Rockett et al 2009).

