-CNS Studies with Intranasal Ketamine: Intranasal ketamine seems a reasonable choice for further studies in the field. Intranasal ketamine has been successfully used in the treatment of headache and pain in ambulatory patients (Kaube et al 2000, Huge et al 2010, Carr et al 2004). In one study, 50 mg of ketamine administered intranasal was well tolerated and led to symptomatic improvement in chronic pain (Carr et al 2004). In psychiatry, Lapidus et al investigated the potential rapid antidepressant effects of intranasal ketamine (50mg) in subjects with MDD. Patients showed significant improvement in depressive symptoms at 24 hours after ketamine compared to placebo. Response criteria were met by 8 of 18 patients (44%) 24 hours after ketamine administration compared with 1 of 18 (6%) after placebo. Intranasal ketamine was well tolerated with minimal psychotomimetic or dissociative effects and was not associated with clinically significant changes in hemodynamic parameters (Lapidus et al 2014).

IRB NUMBER: HSC-MS-17-0903
IRB APPROVAL DATE: 10/09/2019

Scientific Impact: The opportunity to intervene quickly and decisively to prevent suicidal ideation may improve clinical practice and outcomes for subjects at high risk for suicide. A rapid-acting suicide intervention strategy to prevent suicidal ideation and behavior using a feasible and safe route such as the intranasal for ketamine studies, nested with a comprehensive intervention that addresses underlying suicide risk and protective factors, has the potential for enormous public health impact. There is no study evaluating the rapid antisuicidal effects of intranasal ketamine in patients with suicidal ideation. Also, no study has evaluated the role of alcohol abuse as a moderator of clinical response in depression and suicidality.

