Since there is no available studies in this field using the intranasal route and considering that the highest risk times for suicidal behavior are the week after admission to an inpatient psychiatric unit and the week after discharge (Qin & Nordentoft 2005), we aim to investigate the rapid antisuicidal effects of intranasal ketamine in patients with suicidal ideation during depressive episodes with or without recent use of alcohol. We hypothesize that a single dose of intranasal ketamine will induce a rapid, robust and sustained decrease in suicidal ideation in subjects with a comorbid major depressive episode and alcohol dependence relative to only depression and placebo as defined by changes in suicidal ideation scales after 24hrs.

Objectives

Primary objective: To evaluate the rapid antisuicidal effects on a single dose of intranasal ketamine (50mg) in a sample of depression comorbid or not with alcohol abuse compared to placebo.

Secondary objectives:

- To identify clinical variables and dimensions associated with the potential antisuicidal efficacy of intranasal ketamine.
- To identify post-treatment biomarkers associated with the antisuicidal response to ketamine.
- To evaluate the role of recent alcohol abuse in the antisuicidal and antidepressant effects of ketamine
- To identify clinical and biological predictors of response to ketamine
- To evaluate safety and tolerability of intranasal ketamine

Hypothesis:

-Primary: A single dose of ketamine will induce a rapid, robust and sustained decrease in suicidal ideation in subjects with a comorbid major depressive episode and alcohol dependence relative to placebo as defined by change in SSI scale after 24hrs.

-Secondary:

- The antisuicidal efficacy of intranasal ketamine will be independent from its rapid antidepressant efficacy.
- Intranasal ketamine will present superior antisuicidal efficacy in the group with comorbid depression and alcohol compared to depression only.
- Antisuicidal response to ketamine will be correlated with changes in neurotrophic factors and inflammatory markers at one day after ketamine infusion. -Intranasal ketamine (50mg) will be safe and well-tolerated.
- Alcohol use and/or family history of alcohol abuse will be associated with better antisuicidal and antidepressants response to ketamine.

IRB NUMBER: HSC-MS-17-0903

IRB APPROVAL DATE: 10/09/2019

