- 5) *Clinician-Administered Dissociative States Scale* (CADSS) is a clinician-administered measure of perceptual, behavioral and attentional changes occurring during dissociative experiences that has been tested in healthy subjects and post-traumatic stress disorder (PTSD). This scale involves 19 self-reported questions and eight observer ratings scored from 0 (not at all) to 4 (extremely). To characterize dissociative responses to ketamine, the CADSS will be sorted into five subscores with apparent face validity based on published scales that also assess dissociative states: body perception, environmental perception, feelings of unreality, memory impairment and time perception (Bremner et al 1998).
- 6) The *Snaith-Hamilton Pleasure Scale* (SHAPS) is an assessment of anhedonia, which has been extensively used by our group. The 14-item measure takes 5 minutes to complete (Snaith et al 1995).
- 7) The *Clinician-Administered National Institutes of Health-Brief Fatigue Inventory* (NIH-BFI) is an assessment of fatigue in the context of depression (Saligan et al 2015).
- 8) *Self-Report: Alcohol Urge Questionnaire* (AUQ) is a multi-item measure of self- reported urges to drink alcohol, predictor of drinking abuse and relapse (Bohn MJ, Krahn DD, Staehler BA 1995) and AUDIT/CIWA.

Although the primary aim of this study to investigate the efficacy of ketamine as a treatment for suicidal thoughts, this investigation is also designed to provide initial data for potential biomarkers of antisuicidal response and the neurobiology of the response process. Sixty six percent of all patients will

IRB NUMBER: HSC-MS-17-0903
IRB APPROVAL DATE: 10/09/2019

receive intranasal ketamine, while only 33.3% will be receiving placebo. We decided not to use active placebo (midazolam) due to the risk of increasing craving for alcohol. After the end of the trial (48hs), all patients will receive treatment as usual as well as lithium, which is a medication that has shown significant antisuicidal properties (Lewitzka et al 2015). All patients will be discharge when presenting no acute suicidal ideation based on C-SSRS and SSI.

Study Population

All study investigators and raters will be blind to assignment. Subjects will complete an informed consent process and will be systematically screened for inclusion and exclusion criteria, as follows:

Inclusion Criteria:

1. Male or female between the age of 21 and 60 years old, voluntary admission.

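### Inclusion criterion 4 requires current alcohol abuse of every patient, which contradicts the planned groups without it

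*Combined protocol and SAP*

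**What the plan says.** All places are in the combined protocol and SAP.

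**Text that requires alcohol abuse**
- Study Population introduces one list for everyone: "Subjects will complete an informed consent process and will be systematically screened for inclusion and exclusion criteria, as follows". Item 4 of the inclusion criteria is "DSM-IV-TR criteria for current alcohol abuse (but not intoxicated/withdrawal, abstinent from drinking for > 5 days prior to admission". The bracket restricts intoxication, withdrawal and recent drinking. It does not restrict the item to a subgroup.
- Study Procedures gives the pregnancy test to women who satisfy every other inclusion criterion, so the items are cumulative.
- The trial title names comorbid depression and alcohol abuse, and the primary hypothesis concerns patients with a depressive episode and alcohol dependence.

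**Text that plans patients without alcohol abuse**
- General Information: inpatients in a mood episode "with or without comorbid recent abuse of alcohol".
- The aim, in the paragraph before Objectives: ketamine "in patients with suicidal ideation during depressive episodes with or without recent use of alcohol".
- Primary objective: "in a sample of depression comorbid or not with alcohol abuse compared to placebo".
- Secondary hypothesis: "superior antisuicidal efficacy in the group with comorbid depression and alcohol compared to depression only".
- Description of Study Populations: the 30 ketamine patients are split into 15 with and 15 without recent alcohol abuse plus a personal or family history of alcoholism.
- Design: randomisation within a suicide stratum and a suicide-plus-alcohol stratum, making four groups.

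**Text that depends on having both kinds of patient**
- Secondary objective: "To evaluate the role of recent alcohol abuse in the antisuicidal and antidepressant effects of ketamine".
- Background, Scientific Impact, gives as a gap in knowledge that "no study has evaluated the role of alcohol abuse as a moderator of clinical response in depression and suicidality".
- Statistics plans a secondary analysis of recent alcohol abuse and previous dependence.

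**The concern.** The eligibility list and the design describe different populations. A screener who follows the list turns away every patient without current alcohol abuse; one who follows Design enrols them. Two careful readers could therefore recruit different trials.

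The alcohol question is at stake. It is a stated secondary objective, a secondary hypothesis and part of the scientific rationale, and it needs a comparison group that criterion 4 shuts out. If staff enrol that group anyway, each such patient fails a written inclusion criterion and has to be handled as an eligibility deviation.

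**Working it through.** The check has three steps: whether any text limits criterion 4, what follows if it is applied, and how many patients are involved.

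**1. Is the criterion limited anywhere?** The list is introduced once, for all subjects, and is cumulative. Neither the list, Design, Description of Study Populations nor Statistics says that item 4 applies only to the alcohol stratum. Taken as written, eligibility requires items 1 to 7 together, so a patient without current alcohol abuse fails item 4.

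**2. What can then be estimated?** Let T = 1 for ketamine and 0 for placebo, and A = 1 for current alcohol abuse and 0 for none. The four groups in Design are the four combinations of T and A, and the model for treatment, stratum and interaction is

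E(Y) = b0 + b1·T + b2·A + b3·T·A

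| Group | T | A | Possible under criterion 4 as written |
|---|---|---|---|
| Ketamine, alcohol | 1 | 1 | yes |
| Placebo, alcohol | 0 | 1 | yes |
| Ketamine, depression only | 1 | 0 | no |
| Placebo, depression only | 0 | 0 | no |

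- With all four groups filled, the design matrix (1, T, A, T·A) has rank 4 of 4, so all four coefficients are identifiable.
- With A = 1 for everyone, the column A equals the intercept column and T·A equals T. The rank is 2 of 4. Only b0 + b2 and b1 + b3 can be estimated.
- b1 + b3 is the ketamine v placebo difference in comorbid patients, so that comparison survives.
- b2 (recent alcohol abuse) and b3 (its interaction with treatment) cannot be separated from the rest at any sample size. The contrast of comorbid with depression-only patients on ketamine is b2 + b3, and it is lost too.

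**3. How many patients?** Description of Study Populations plans 15 of 30 ketamine patients without recent alcohol abuse: 15/30 = 50%. If that subgroup means no current abuse (assumption), the number eligible under criterion 4 is 0 instead of 15. The same section does not split its 15 placebo patients by alcohol, so the placebo count could be anything from 0 to 15 on its text alone.

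The sample-size statement in Statistics concerns ketamine v placebo response. It does not use the strata, and no figure in it changes.

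**The case against.** **The intent is plain.** The strata are described in several places, and a reader would take item 4 as meant for the alcohol stratum. That is probably so for most readers. But the title and the primary hypothesis agree with item 4 as it stands, so a reader could equally conclude that only comorbid patients are wanted. The slip does not correct itself.

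**The list is not the only source of eligibility.** Design adds a threshold on MADRS item 10, and Human Subjects Protection excludes cognitively impaired persons; neither is in the list. This stands: nothing ranks the list above Design. It makes the problem a conflict between passages and does not show that Design overrides item 4.

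**Practice may be sound.** Staff screen with an Inclusion/Exclusion Checklist and a Study Summary, which may carry the qualifier. They are not in the documents. A reader might infer that depression-only patients were in fact turned away or wrongly enrolled; the documents do not show either.

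**The figure of 15 is not firmly documented.** The subgroup wording joins recent abuse to personal or family history. If both are required for the alcohol subgroup, a patient with current abuse but no such history could belong to the other one, and zero would not follow from that section. This stands, and is why the figure is given as conditional. It does not remove the conflict with the depression-only hypothesis or with the two strata in Design.

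**The damage is limited.** Also correct. Variation in family history and previous dependence would remain. A reader might infer that the main efficacy comparison fails; it does not, although it would describe comorbid patients only.

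**Conclusion.** The inconsistency is real. As written, criterion 4 excludes patients whom the aim, the primary objective, a secondary hypothesis, the subgroup plan and the randomisation scheme all require. If it is followed, two of four groups are empty and the recent-alcohol-abuse effect and interaction are not estimable. If it is not followed, depression-only patients are eligibility deviations. About 15 planned ketamine patients are affected, on the assumption about the subgroup wording stated above.

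A reader might go further and say that criterion 4 itself is the error. Most of the text favours that, but the title and primary hypothesis do not, so the documents alone do not settle the direction.

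Confidence is high in the textual conflict and lower in its practical effect, which depends on the unseen checklist. This should be fixed, but it does not prevent the treatment comparison.

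**What to change.** Reconcile the passages in one amendment.

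**If both kinds of patient are intended**, as most of the text supports:
1. Limit the alcohol-abuse requirement in criterion 4 to the alcohol stratum, and state that patients without it are eligible for the depression-only stratum.
2. State how current abuse, dependence, and personal or family history define the alcohol stratum. The sections use these terms differently.
3. State whether the intoxication, withdrawal and abstinence wording applies to both strata, so that the edit does not drop it from one by accident.

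**If only comorbid patients are intended**, leave criterion 4 and revise General Information, the aim, the objectives, the secondary hypotheses, the subgroup and stratum descriptions, and the alcohol analysis in Statistics.

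In either case, check that the Inclusion/Exclusion Checklist and Study Summary match the amended text.

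The first route costs a change to one criterion, the clarifying statements and a checklist check. The second touches more sections. Neither adds procedures. The documents do not give enrolment status, and an amendment would not reclassify patients already enrolled.
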